## **Effects of Beta-Caryophyllene Supplementation on Autonomic Regulation and Apnea Performance in Elite Divers - a Randomized Crossover Trial**

**Document Date: Jan 05 2026**

**IRB approved date: June 1, 2025**

### **Project summary**

This project recruited 15–20 healthy adult male active freedivers. Using a randomized crossover design with double-blind methodology, participants were assigned to either the  $\beta$ -caryophyllene trial (BCP) trial or the placebo (PLA) trial, which without  $\beta$ -caryophyllene. Participants consumed either 200 mg of  $\beta$ -caryophyllene capsules (BCP trial) or placebo capsules (PLA trial) based on pre-test results. After a 30-minute rest period and warm-up, a single maximal voluntary static breath-hold test was conducted. Breath-hold duration and physiological and salivary biochemical indicators before and after the breath-hold test were observed.

### **Introduction**

Currently, no specific nutritional supplements have been established internationally to enhance athletic performance in freediving. Activation of the cannabinoid receptor type 2 (CB2) may represent a significant approach to further enhance freediving capabilities. Therefore, this study investigates the effects of  $\beta$ -caryophyllene (BCP) supplementation on static apnea performance by examining its influence on CB2, which may improve autonomic nervous system function and increase pain tolerance.

### **Methods**

#### **Study design**

This study employed a randomized crossover design with double-blind methodology, dividing subjects into either the  $\beta$ -caryophyllene trial (BCP) group or the placebo trial (PLA) group without  $\beta$ -caryophyllene. Testing occurred during the off-season. Excel software randomly assigned participants to groups and generated unique identification numbers for each subject. The experimental sequence was determined through random allocation. Three days prior to the first formal experiment, subjects were instructed to record all dietary intake and consume identical meals during subsequent formal experiments. Each experiment commenced at 9:00 AM, with subjects required to arrive at the laboratory in a fasting state for testing.

#### **Participants**

This study plans to recruit 15–20 healthy adult males with training in freediving or long-distance swimming as subjects. According to the International Association for the Development of Apnea (AIDA) classification system, inclusion criteria are: 1. At least 3 years of training in freediving or long-distance swimming, with the highest AIDA certification level (Level 4). 2. Absence of cardiovascular or joint diseases. 3. Recovery from sports injuries such as strains or sprains for at least 3 months. Exclusion criteria are: 1. Insufficient training duration. 2. Presence of cardiovascular or joint diseases, or any conditions susceptible to exercise-induced damage. 3. Female or underage subjects. 4. Individuals allergic to  $\beta$ -caryophyllene. The consent form is completed after the participant has given consent. This study was conducted following the Declaration of Helsinki.

## Protocol

All formal experiments are scheduled to begin at 9:00 AM, with subjects arriving at the laboratory in a fasting state. After a brief rest period, the first saliva sample is collected. Subjects are connected to a gas analyzer and heart rate monitor, and their resting metabolic rate, heart rate, and heart rate variability are recorded for 10 minutes in a supine position. Following this, subjects ingest either  $\beta$ -caryophyllene (BCP group) or a placebo capsule (PLA group). After a period of quiet rest, the same measurements are taken again.

Following this, subjects ingest either  $\beta$ -caryophyllene (BCP trial) or a placebo capsule (PLA trial). After resting quietly, a second 10-minute recording of resting energy expenditure, heart rate, heart rate variability, and a second saliva sample are collected in the supine position. Based on pre-test results,  $\beta$ -caryophyllene exhibited optimal efficacy 30 minutes post-administration. Thus, subjects rested quietly for 30 minutes. During this period, subjects continuously wore gas analyzers and heart rate monitors, with near-infrared spectroscopic cerebral oximetry (NIRS) sensors attached to the frontal lobe. NIRS cerebral oximetry) on the forehead to measure cerebral oxygenation. A pulse oximeter was attached to the fingertip. Subsequently, participants performed a maximal static breath-hold test following three submaximal breath-holds, replicating the protocol of Hoiland et al. (2017) (1).

## $\beta$ -Caryophyllene capsules and placebo

The same brand of  $\beta$ -caryophyllene has also been used in previous studies (2). Using dried, purified  $\beta$ -caryophyllene powder, subjects received optimized  $\beta$ -caryophyllene supplementation doses based on preliminary testing results, administered via capsules.

lacebo capsules contained flour. All preparation processes were completed by non-experimental staff and provided to experimental staff through numbering to achieve double-blind conditions.

### **Saliva sample collection and analysis**

Saliva samples were stored in a refrigerator at -80 degrees immediately after collection. For analysis, samples were thawed and centrifuged at 4000 rpm for 5 min. 500  $\mu$ L of saliva samples were transferred to glass tubes for mass spectrometry analysis and Enzyme-linked immunosorbent assay (ELISA) analysis respectively. The analysis of saliva  $\alpha$ -amylase concentration was conducted utilising an enzyme-linked immunosorbent assay (ELISA) with commercially available reagents (Neogen Corporation, Kentucky, USA; Salimetrics LLC, State College, PA, USA).

### **Statistical analysis**

All data are presented as means  $\pm$  standard deviations. The Shapiro–Wilk test was utilised to evaluate the normality of the data. The grip strength and number of fall on each rounds between the two trials were analyzed using paired t-tests. The saliva caffeine and  $\alpha$ -amylase concentration and RPE were analyzed using two-way ANOVA with repeated measures. If the interaction effect (trial  $\times$  time) were significant, the Bonferroni method was used to perform post hoc comparisons. Effect sizes were calculated using Cohen's d to quantify the magnitude of observed effects and defined as trivial ( $<0.20$ ), small ( $0.20$ – $0.40$ ), moderate ( $0.40$ – $0.80$ ), and large ( $>0.8$ ), respectively. The power value of each data was conducted using G\*Power 3.1.9.6 software (3).

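### The statistical analysis section assigns tests to outcomes this trial does not describe collecting, and none to breath-hold duration

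*Protocol*

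**What the plan says.** The title sets the subject: "Effects of Beta-Caryophyllene Supplementation on Autonomic Regulation and Apnea Performance in Elite Divers". The Introduction gives the aim as the effect of "supplementation on static apnea performance by examining its influence on CB2". The Project summary announces the outcomes: "Breath-hold duration and physiological and salivary biochemical indicators before and after the breath-hold test were observed".

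The section headed Protocol describes the measurements. Before ingestion, "their resting metabolic rate, heart rate, and heart rate variability are recorded for 10 minutes in a supine position". After ingestion and rest there is "a second 10-minute recording of resting energy expenditure, heart rate, heart rate variability, and a second saliva sample are collected in the supine position". Cerebral oxygenation (NIRS) and fingertip oximetry are added, and then "participants performed a maximal static breath-hold test following three submaximal breath-holds". The saliva section describes alpha-amylase by ELISA and a mass spectrometry assay with no named analyte.

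The Statistical analysis section assigns tests in two sentences. The first is "The grip strength and number of fall on each rounds between the two trials were analyzed using paired t-tests". The second begins "The saliva caffeine and" and goes on to alpha-amylase and RPE, all three assigned to a two-way repeated-measures ANOVA. The rest of the section is generic: means and standard deviations, a normality check, Bonferroni post hoc comparisons after a significant interaction, Cohen's d, and a power calculation in named software.

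**The concern.** The outcomes in the statistical section do not belong to the experiment in the rest of the document. Falls counted by round cannot arise from one static breath-hold, and neither grip strength nor caffeine has any role in the procedures described. The variable the trial exists to study has no between-trial comparison.

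Two things are at stake. First, anyone following the section literally would look for variables that are not there and would never compare breath-hold time between beta-caryophyllene and placebo. Second, the protocol gives no protection against selective reporting. With no applicable test and no primary outcome stated, the choice among breath-hold time, heart rate variability, cerebral oxygenation and saturation stays open as far as this document goes. Heart rate variability and NIRS each offer several indices, which widens that choice.

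**Working it through.** The protocol states no figure to reproduce, so the check sets the outcomes described as measured against those assigned a test.

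| Outcome | Described as measured? | Test assigned? |
|---|---|---|
| Breath-hold duration | Yes (Project summary; Protocol section) | No |
| Resting metabolic rate / energy expenditure | Yes (Protocol section) | No |
| Heart rate | Yes (Protocol section) | No |
| Heart rate variability | Yes (Protocol section) | No |
| Cerebral oxygenation (NIRS) | Yes (Protocol section) | No |
| Fingertip oximetry | Yes (Protocol section) | No |
| Saliva alpha-amylase | Yes (saliva section) | Yes, ANOVA |
| Grip strength | No | Yes, paired t-test |
| Falls per round | No | Yes, paired t-test |
| Saliva caffeine | Not named (one mass spectrometry analyte is unspecified) | Yes, ANOVA |
| RPE | No | Yes, ANOVA |

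- Outcomes with a test: 5. Described as measured: 1 (alpha-amylase). Not described: 5 − 1 = 4.
- Outcome groups measured: 7. With a test: 1. Without: 7 − 1 = 6.

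The generic sentences do not close the gap. Describing all data by mean and standard deviation, checking normality and reporting Cohen's d could all be applied to breath-hold duration, but none of them assigns it a comparison between trials. The Bonferroni step covers only post hoc comparisons after a significant trial-by-time interaction. It gives no control across outcomes.

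To illustrate what is at risk when no outcome is designated primary, suppose each of the seven measured groups were tested at 0.05. The protocol states no significance level, so 0.05 is an assumption. With independent tests, the chance of at least one false positive is 1 − 0.95^7 = 1 − 0.698 = 0.302, about 30%. With perfectly correlated tests it is 5%. These outcomes come from the same subjects and partly from the same devices, so the true value probably lies between the two. The finding does not depend on this figure.

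**The case against.** The strongest objection is that a separate statistical analysis plan may exist and may specify breath-hold duration properly. That would excuse silence, and it does weaken any complaint that the protocol merely omits a primary outcome. It does not excuse this section, which positively assigns tests to outcomes the trial does not describe. A sound analysis plan would then contradict the protocol, and the section would still need correcting.

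Several narrower points stand as qualifications:

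- That the text was carried over from another study is an inference. What can be shown is that the outcomes do not match this trial.
- Caffeine is undescribed rather than excluded, because the mass spectrometry analyte is unnamed. The count with no trace at all is three (grip strength, falls, RPE), plus one unresolved.
- RPE might be collected without being described.
- Alpha-amylase does have a test, and the title also covers autonomic regulation. The safe statement is therefore that apnea performance is never tested, not that nothing in the title is.
- The 30% figure rests on one grouping of outcomes and on independence. It is an upper illustration and not a property of the plan.
- The title names autonomic regulation first, so the choice of primary outcome is finally the sponsor's. The Introduction and Project summary point to breath-hold performance.

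None of these removes the mismatch.

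**Conclusion.** The concern holds. Four of the five outcomes given a test are not described as collected, and six of the seven measured outcome groups have no test. Breath-hold duration, the outcome the Introduction and Project summary put first, is among the six. This is an error in an existing statistical section, and as written the section cannot answer the trial's main question. It must be fixed.

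The counts rest on the protocol alone and on reading its procedures as complete. If caffeine turns out to be the unnamed mass spectrometry analyte, or RPE is collected without description, the first count falls accordingly. Breath-hold duration would still have no test.

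**What to change.** Replace the two outcome sentences in the Statistical analysis section.

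1. Name breath-hold duration in the single maximal static apnea as the one primary outcome, compared between beta-caryophyllene and placebo within subject at two-sided 0.05.
2. List heart rate, named heart rate variability indices, resting metabolic rate, cerebral oxygenation, oxygen saturation and saliva alpha-amylase as secondary outcomes, each with its time points and its test.
3. Delete grip strength, falls, rounds, caffeine and RPE. If any of them is really collected, describe its measurement in the procedures instead.
4. Name the mass spectrometry analyte or drop that assay.
5. Before fixing the time points, reconcile the saliva schedule. The Project summary places the salivary indicators before and after the breath-hold, while the Protocol section describes samples only before and after ingestion.

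This means rewriting one paragraph and tidying the saliva schedule, with no added participants or procedures. The price is that only one outcome can then carry the efficacy claim.

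Timing also matters. The document is dated January 2026, ethics approval was June 2025, and the text says both that participants were recruited and that recruitment is planned. If data already exist, rewording cannot restore pre-specification. The change should then be dated, and should state whether it was made before unblinding.

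### Salivary alpha-amylase is judged by a trial-by-time interaction when adjusting for the pre-dose sample taken at each visit would usually be more precise

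*Protocol*

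**What the plan says.** The Protocol's Study design section describes a two-treatment crossover: "This study employed a randomized crossover design with double-blind methodology". The Participants section sets the size: "This study plans to recruit 15–20 healthy adult males with training in freediving or long-distance swimming as subjects".

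The section headed Protocol puts a saliva sample on each side of ingestion at every visit. Before the capsule: "After a brief rest period, the first saliva sample is collected". After the capsule and a rest: "a second saliva sample are collected in the supine position". Each subject therefore has a pre-dose and a post-dose alpha-amylase value under both BCP and placebo.

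The Statistical analysis section fixes the method. Salivary caffeine and alpha-amylase "concentration and RPE were analyzed using two-way ANOVA with repeated measures". If the interaction of trial and time is significant, "the Bonferroni method was used to perform post hoc comparisons". The pre-dose value is thus one level of the time factor, that is, part of the outcome. No baseline covariate is named.

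**The concern.** In a two-by-two layout of trial and time, the interaction subtracts the whole pre-dose difference from the post-dose difference. If the two differences are only moderately correlated, the subtraction adds more noise than it removes. The trial main effect does not help, because it averages the pre-dose difference, where no effect is possible, with the post-dose difference and so halves any effect.

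In a crossover, the correlation that matters is not the familiar one between a person's two amylase values. A subject's stable level cancels when placebo is subtracted from BCP, so what remains is visit-specific variation. A high raw correlation does not guarantee a high r.

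At stake is the precision of the alpha-amylase comparison in a trial of 15 to 20 men, and the chance that a real effect fails the interaction test and is not followed up.

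**Working it through.** **Inputs from the Protocol.** n = 15 to 20 (Participants); one pre-dose and one post-dose saliva sample per visit (section headed Protocol); interaction test with conditional follow-up (Statistical analysis). The protocol gives no sample-size calculation with inputs, so there is no stated figure to reproduce.

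**Assumptions.** Two-sided 5% level; r = 0.3, 0.5, 0.7 (wider range where noted); a true effect of 0.7 SD of the paired post-dose difference; equal variance s² of the two differences; normal data; no period effect.

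**Step 1: the two contrasts.** Let D_pre and D_post be a subject's BCP-minus-placebo differences before and after dosing, with correlation r.

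- Interaction: mean of D_post − D_pre, variance 2(1 − r)s²/n. This fixes the baseline slope at 1.
- Adjusted: intercept of the regression of D_post on D_pre. With the slope known, the variance is (1 − r²)s²/n. Estimating it multiplies this by (n − 2)/(n − 3).

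**Step 2: variance ratio, adjusted to interaction.** (1 − r²)/[2(1 − r)] × (n − 2)/(n − 3) = (1 + r)/2 × (n − 2)/(n − 3). The last factor is 13/12 = 1.083 at n = 15 and 18/17 = 1.059 at n = 20.

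| r | (1 + r)/2 | n = 15 | n = 20 |
|---|---|---|---|
| 0.3 | 0.65 | 0.70 | 0.69 |
| 0.5 | 0.75 | 0.81 | 0.79 |
| 0.7 | 0.85 | 0.92 | 0.90 |
| 0.9 | 0.95 | 1.03 | 1.01 |

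Simulation with 20,000 runs per case agrees: 0.72, 0.82, 0.92 and 1.03 at n = 15; 0.69, 0.80, 0.90 and 1.01 at n = 20.

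**Step 3: break-even.** The ratio reaches 1 when (1 + r)/2 = (n − 3)/(n − 2). At n = 15, r = 2 × 12/13 − 1 = 0.85. At n = 20, r = 2 × 17/18 − 1 = 0.89.

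**Step 4: power at 0.7 SD.** The interaction uses the non-central t with n − 1 degrees of freedom and non-centrality 0.7√n/√[2(1 − r)]. For n = 15 and r = 0.3 this is 0.7 × 3.873/1.183 = 2.29. The adjusted test was simulated with the slope estimated and n − 2 degrees of freedom.

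| n | r | Interaction | Adjusted |
|---|---|---|---|
| 15 | 0.3 | 57% | about 72% |
| 15 | 0.5 | 71% | about 80% |
| 15 | 0.7 | 90% | about 92% |
| 20 | 0.3 | 71% | about 86% |
| 20 | 0.5 | 84% | about 91% |

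These figures do not include the degree of freedom for a period term.

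**Step 5: interval width at n = 15.** In units of s, the mean simulated half-width falls from 0.645 to 0.542 at r = 0.3 (1 − 0.542/0.645 = 16% narrower) and from 0.544 to 0.492 at r = 0.5 (10% narrower).

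**Step 6: validity.** With no true effect and r = 0.5, both tests rejected in about 5% of simulated trials at n = 15 and n = 20.

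**The case against.** **The ANOVA is a valid analysis.** This stands. Type I error is held, so a reader who inferred bias or a wrong test would go too far. The question is precision only.

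**Adjustment does not always win.** This stands too. The large-sample ratio (1 + r)/2 is below 1 for every r under 1, so a reader might infer that adjustment is never worse apart from a degree of freedom. With 15 subjects, estimating the slope costs more than that: at r = 0.9 the variance is about 3% higher. Neither r nor the effect size is in the protocol, so the benefit runs from sizeable to none.

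**The number of saliva samples is not certain.** The Project summary says "physiological and salivary biochemical indicators before and after the breath-hold test were observed", which may mean a sample after the breath-hold as well. Time would then have three levels and the interaction would be a 2-df omnibus test. Simulated at n = 15 with an effect of 0.78 SD in both later samples, its power against a single adjusted comparison was 54% against 77% at r = 0, 85% against 87% at r = 0.5, and 98% against 96% at r = 0.7. The advantage shrinks and can reverse.

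**Other outcomes are not covered by the stated method.** Before dosing, "their resting metabolic rate, heart rate, and heart rate variability are recorded for 10 minutes in a supine position", and these are recorded again afterwards. A reader might infer that they share the weakness and that the autonomic part of the title rests on it. The Statistical analysis section names no method for them, and a statistical analysis plan not shown here may do so. The point therefore holds for alpha-amylase only, which is not named as primary.

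**The section has larger problems.** It analyses grip strength, falls and salivary caffeine, which the procedures do not describe, and gives no method for breath-hold duration. That makes this point secondary, but does not remove it: alpha-amylase is measured, and its method is stated in the protocol rather than left open.

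**Conclusion.** The point holds as an efficiency weakness limited to alpha-amylase. With one pre-dose and one post-dose sample per visit, baseline adjustment cuts the variance by roughly 30% at r = 0.3, 20% at r = 0.5 and 8 to 10% at r = 0.7, across 15 to 20 subjects. Beyond the break-even correlations it gives nothing. At an assumed effect of 0.7 SD, the gain in power is about 15 percentage points at r = 0.3 and 7 to 9 at r = 0.5.

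All of this rests on an assumed r, equal variances, two time points and no period effect. With a third sample the figures do not apply directly. The documents do not support a claim that the planned test is invalid, that adjustment is better at every correlation, or that the analyses of heart rate, heart rate variability or metabolic rate are faulty. Label: cheap improvement.

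**What to change.** For alpha-amylase, replace the interaction test in the Statistical analysis section with a regression of the BCP-minus-placebo post-dose difference on the BCP-minus-placebo pre-dose difference, with a period term, or fit the equivalent mixed model. Report the adjusted BCP-minus-placebo difference with its 95% confidence interval, and do not make this comparison conditional on a significant interaction. State how many saliva samples are taken per visit and which post-dose sample the comparison uses.

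As a suggestion only, the same model suits heart rate, heart rate variability and resting metabolic rate, which are also recorded before and after dosing.

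Cost: a sentence or two of text and no new data; one degree of freedom for the covariate, one for the period term, and the small cost of estimating the slope, which becomes a net loss of about 3% in variance at n = 15 if r is near 0.9.
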